#### 5.2 Numerator for VTR

Fetuses will be regarded as vertically infected if fetal or placental tissue, or amniotic fluid, tests PCR+. Children will be regarded as vertically infected on the basis of IgM or PCR evidence within 7 days of delivery. Infants who lose antibody will be regarded as not vertically infected: this includes infants in whom a falling IgG titer is observed as well as those who become IgG-.

There are reports of children with clinical signs of congenital infection, such as microcephaly, whose mothers were infected in pregnancy, but in whom no laboratory evidence of congenital ZIKV can be obtained from testing serum and CSF for IgM and PCR. Definitions of congenital zika in the absence of laboratory evidence are being developed [2, 3], which may be revised as new data becomes available. Although the evidence is not clear at the time of writing, it seems likely that these infected children will remain IgG antibody positive.

Infants who are IgG antibody positive when last seen may be congenitally infected. The probability that they are congenitally infected depends on two factors: firstly, their age, because maternal antibody declines over time and is usually absent within 15 months. Secondly, the risk of post-natal

Author: [name] (UNIVBRIS)

15

infection. Appendix 5 describes statistical analyses that use data on antibody loss in control children born to IgG+ mothers, and data on post-natal infection on initially IgG- newborns, to estimate the probability of vertical infection in all IgG+ infants whose infection status cannot otherwise be determined.

It remains possible either that congenital infection can take place, causing damage, and clearing prior to delivery and leaving no laboratory markers; or that maternal infection affects fetal development without crossing the placenta. It is for this reason that ZIKA-VT includes a 2nd control group, of children born to mothers with no infection in pregnancy.

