#### 5.3 Gestational age (GA) at maternal infection

In a full data analysis, the target parameter here is not a single date, but a *probability distribution* for each woman, representing when the onset of infection was likely to have occurred, relative to the date of conception which may itself be imperfectly known. To simplify presentation in this SAP we represent this as a discrete distribution in units of one week. Information on the distribution of GA at infection will be derived from one or more of the following

- (a) the date of symptoms, if reported
- (b) dates of a first PCR+ test result and subsequent PCR results
- (c) seroconversion, between last IgG- and first subsequent IgG+
- (d) dates of a first IgM+ and subsequent IgM tests
- (e) dates of an initial IgG+ followed by a rising IgG titer subsequent IgG tests
- (f) avidity tests may also be used to help estimate date of infection, especially in samples that are IgM+ and/or IgG+ at recruitment

Note that an initial PCR+ or IgM+ test result is only informative about timing of infection to the extent that the population distributions of PCR persistence and IgM persistence are known. Thus, test persistence information will be critical in estimating GA at maternal infection (see *Section 7.4*).

In practice, if the tests all had perfect sensitivity and specificity, the sequence of test results would either indicate no maternal infection during pregnancy, or it would define an *interval* during which infection has occurred. The persistence distributions, if relevant, will impact on the probability distribution of GA at infection *within* that interval. The issue of test accuracy adds a further layer of complexity, discussed in the next section.

A third source of information is the weekly local surveillance of incident cases of confirmed or suspected ZIKV, DENV and CHIKV [4]. If we reasonably assume that the attack rates in the general population are proportional to attack rates in the pregnant women being recruited, the surveillance data represents an *a priori* distribution of GA at maternal infection within the interval defined by the sequence of tests. The PCR or IgM persistence distributions, if relevant, will combine with the surveillance information to define maternal GA at infection.

Author: [name] (UNIVBRIS)

16

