### 7.5 Using ZIKA-VT data to update prior information on test persistence

The previous section has shown how, given information on test persistence, the date of a positive PCR or IgM test informs the GA of maternal infection. In this section, we show how to estimate the distribution of test persistence from ZIKA-VT data, or, more usefully, how to update any prior information available.

Simplifying assumptions have been made for purposes of clarity and in order to keep the notation minimal: for example, that the date of onset of symptoms is taken to be the date of the onset of infection, and that tests are positive from that date. Adjustments can, and will, be made to accommodate these factors, but at this stage greater veracity would be at the expense of clarity.

 $F(d,\theta)$  is defined for d=1,2...D where D is the maximum possible duration of that marker. The data generated by ZIKA-VT and similar studies is *doubly interval censored*, because in most cases neither the onset of the marker response, nor the end of the marker response, is observed. Methods for analysis of doubly interval censored data have been published [5, 6] and have been applied to the timing of maternal infection in the context of congenital toxoplasmosis [7, 8]. A recent paper [9] includes a brief up-to-date review of the most commonly used methods.

ZIKV and the ZIKA-VT protocol have features that require extensions and modifications to existing methods. First, not only is incidence changing over time, but each individual woman is exposed to a different incidence which varies over the course of her pregnancy. Second, information on multiple markers in multiple types of samples will need to be processed simultaneously.

We begin with an analysis for a single marker, then we consider how to handle variables that might affect persistence, such as previous infection or the presence of symptoms, and finally the joint analysis of multiple markers.

[figure not shown]

Author: [name] (UNIVBRIS)

21

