#### 8.1 Analyses to be carried out

Note that the estimates of incidence and seroprevalence that can be generated directly from ZIKA-VT are not true population estimates, because, within each collaborating center, the intention is to recruit pregnant women from areas at higher risk of arbovirus infection, and during periods of higher incidence. However, there is an interest in estimating incidence because it may correlate with risk of transmission or adverse clinical outcomes, if for example, both are related to viral load or degree of susceptibility.

All analyses will be initially stratified by center and mosquito season, or by center and year if there is no mosquito season. The text under each heading below should be understood as specifying one or more tables, in most cases separately for each of the three arboviruses.

8.1.1 Basic demographics of the sampled population. We will tabulate the numbers recruited each season, their age distribution. Further breakdowns will be by: socio-economic class, income range, type of housing, area of residence, residence stratified by arbovirus infection incidence (from surveillance data), as considered appropriate

8.1.2 Seroprevalence and cumulative incidence. For each arbovirus, the denominator for a seroprevalence estimate is the number of women who had at least one IgG test, and the numerator is the number who were IgG+ on their first test. In addition to "crude" (without adjustment) estimates of seroprevalence, we will obtain estimates of cumulative incidence  $\pi$ , which is (observed) seroprevalence p adjusted for IgG sensitivity and specificity, using the relationship

$$p = \pi Se + (1 - \pi)(1 - Sp)$$

Author: [name] (UNIVBRIS)

26

The sensitivity and specificity will be characterized as probability distributions based on the data available, assembled under the ZIKA-VID work package. The sources of this data will be continually updated (see *Appendix 4*).

If more than one test was used, results will be reported separately for each test (see Table 5)

The adjustment can be extended to account for cross-reactivity between DENV and ZIKV IgG tests, given information on sensitivity, general false positive rates, and cross-reactivity of both assays:

$$p_{Z} = \pi_{Z} S e_{Z} + (1 - \pi_{Z})(1 - S p_{Z}) + \pi_{D} X r_{Z}$$

$$p_{D} = \pi_{D} S e_{D} + (1 - \pi_{D})(1 - S p_{D}) + \pi_{Z} X r_{D}$$

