## APPENDIX 5. Role of Antibody persistence in diagnosis of congenital infection

The criteria for congenital infection (CI) are: PCR+ in serum, urine or CSF OR IgM+ in serum, urine or CSF; OR congenital zika syndrome meeting an agreed definition (see *Section 5.2*) Infants who lose IgG antibody, or who have consistently falling IgG titers, will be regarded as not CI.

The remaining children are those that remain IgG+ at last follow up. They have a probability of being congenitally infected that increases with time, but it is necessary to take into account that they may have acquired antibody following a post-natal infection.

Suppose we have available information on the probability Ab(t) that an uninfected child born to an antibody +ve mother remains IgG+ t weeks after delivery. Suppose also that we have information on the probability Pn(t) that an initially IgG- newborn is IgG+ t weeks after birth as a result of a postnatal infection.

Now consider the babies born to women infected in pregnancy: all will be initially lgG+. The proportion lgG+ at time t is:

$$X(t) = (V + (1-V)Ab(t)) + (1-V-(1-V)Ab(t))Pn(t)$$

If there was no post-natal acquisition of antibody, we should observe X(t) fall off to an asymptote V representing the vertical transmission rate. Instead we expect X(t) to fall until all maternal antibody is lost, and then continue to rise in response to postnatal acquisition. As we can observe Ab(t) and X(t), and we have data on and Pn(t), we can recover an estimate of V.

If AB(t) indicates having IgG antibody at time t, then the probability that a child who is IgG+ at age t is CI is:

$$p(CI \mid AB(t)) = \frac{p(AB(t) \mid CI).p(CI)}{p(AB(t) \mid CI).p(CI) + p(AB(t) \mid \overline{CI}).p(\overline{CI})}$$
$$= \frac{V}{V + (1 - Ab(t))V}$$

These analyses can be extended to include covariates, and can be integrated into the calculation of the vertical transmission rate (Section 7.1) [14].

Data on Ab(t) will be generated from within ZIKA-VT, but we will also refer to other sources of information as listed in the following table, which will be updated regularly:

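### Appendix 5 indexes post-natal infection by infant age alone and borrows it from IgG-negative newborns; where incidence changes over the birth period, this can bias the antibody-based part of the VTR in either direction

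*SAP*

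**What the plan says.** Appendix 5 of the SAP deals with infants who are still IgG+ when last seen. It defines Pn(t) as the probability "that an initially IgG- newborn is IgG+ t weeks after birth as a result of a postnatal infection"; Section 5.2 describes the same source as "data on post-natal infection on initially IgG- newborns". The appendix then turns to the target group ("Now consider the babies born to women infected in pregnancy"), all of whom start IgG+, and writes the proportion IgG+ at age t as

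X(t) = V + (1−V)Ab(t) + (1−V)(1−Ab(t))Pn(t),

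where Ab(t) is the probability that an uninfected child still carries maternal antibody. With X, Ab and Pn in hand, "we can recover an estimate of V". The appendix allows extension to covariates and integration into Section 7.1, but names neither calendar time nor center.

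Elsewhere the SAP treats calendar time as essential. Section 7.5 says of the mothers that "not only is incidence changing over time, but each individual woman is exposed to a different incidence". Section 5.3 uses "weekly local surveillance of incident cases of confirmed or suspected ZIKV, DENV and CHIKV" to time maternal infection. Section 8.1 stratifies the population analyses by center and season and says that the intention is to "recruit pregnant women from areas at higher risk of arbovirus infection, and during periods of higher incidence".

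**The concern.** An infant's chance of post-natal infection depends on the calendar weeks lived through and on the place, not only on age. Pn(t) is learned in one group of infants and used in another whose mothers were infected in pregnancy. Women are infected in proportion to incidence, so births to infected mothers cluster during and after high-incidence weeks, whereas IgG- newborns may also come from before a wave. If a wave passes and incidence then falls, the borrowed Pn is too large for the infants being analyzed and V comes out too low. If incidence rises over the birth period, the infants of infected mothers meet more infection after birth than the pooled controls did, and V comes out too high.

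Section 5.2 says maternal antibody is usually gone within 15 months, so the informative IgG+ results come after a long exposure window. The result matters because Table 1 counts persistent antibody as vertical infection, Section 7.3 relies on it for severe cases without other laboratory evidence, and Section 1.3 ranks the VTR as the most important target parameter. Centers with different epidemic curves could also appear to differ in VTR when they differ only in post-natal exposure.

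**Working it through.** **Nothing to reproduce.** The SAP states no value for V or Pn(t). V, Pn and the incidence curves below are assumptions, shown over a range.

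**Formula.** Take an age at which maternal antibody has gone (Ab = 0; 15 months, about 65 weeks). Then X = V + (1−V)·Pn_true. Inverting with the Pn actually used gives

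V̂ = (X − Pn_used)/(1 − Pn_used), equivalently 1 − V̂ = (1−V)(1−Pn_true)/(1−Pn_used).

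If Pn_used = Pn_true, then V̂ = V exactly.

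**Plausible scale of Pn.** Section 7.6 uses 10% and 1% of women infected per pregnancy as illustrations. Spread evenly over 42 weeks and carried to 65 weeks:
- 1 − 0.90^(65/42) = 15.0%
- 1 − 0.99^(65/42) = 1.5%

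**Direct substitution:**
- V = 10%, Pn true 2%, used 10%: 1 − 0.90×0.98/0.90 = 2.0%
- V = 10%, Pn true 10%, used 2%: 1 − 0.90×0.90/0.98 = 17.3%
- V = 20%, the same two pairs: 12.9% and 26.5%
- V = 30%, the same two pairs: 23.8% and 35.7%

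**Mismatch produced by calendar time.** A deterministic model with weekly incidence waves compared infants of women infected in the 40 weeks before birth (Pn true) with IgG- newborns of never-infected women (Pn used). Each group was averaged over its own birth dates, at age 65 weeks. Cells show V̂, with V̂/V in brackets; Pn is rounded.

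| Assumed incidence and births | Pn true | Pn used | V = 10% | V = 20% | V = 30% |
|---|---|---|---|---|---|
| One 20% wave, births over two years around it | 2.5% | 8.8% | 3.8% (0.38) | 14.5% (0.72) | 25.2% (0.84) |
| One 30% wave, same births | 4.0% | 14.1% | −0.6% (−0.06) | 10.6% (0.53) | 21.8% (0.73) |
| Falling annual waves 20%, 5%, 5%, one year of births | 10.6% | 18.1% | 1.8% (0.18) | 12.7% (0.64) | 23.6% (0.79) |
| Rising annual waves 5%, 20%, 20%, one year of births | 20.8% | 13.1% | 18.0% (1.80) | 27.1% (1.35) | 36.2% (1.21) |
| 3% wave then 30% wave, births over 100 weeks | 27.7% | 13.5% | 24.8% (2.48) | 33.2% (1.66) | 41.5% (1.38) |
| One 30% wave, births from just before its peak | 3.8% | 5.7% | 8.2% (0.82) | 18.4% (0.92) | 28.6% (0.95) |
| One 30% wave, births from peak to 40 weeks later | 2.6% | 3.4% | 9.3% (0.93) | 19.4% (0.97) | 29.5% (0.98) |
| Equal annual waves of 10% | 11.7% | 12.3% | 9.5% (0.95) | 19.5% (0.98) | 29.6% (0.99) |
| Constant incidence | 15.0% | 15.0% | 10.0% (1.00) | 20.0% (1.00) | 30.0% (1.00) |

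As a check on the first row: 1 − 0.90×0.975/0.912 = 3.8%. At V = 5% the same scenarios run from a negative estimate to about 4.1 times the true value.

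**The case against.** Appendix 5 is a sketch. It does not say that Pn will be pooled over centers or periods, and its covariate sentence leaves room for the remedy. Section 3.1 says post-natal incidence in the control groups may assist the VTR analysis, and that post-natal infection will be seen in children of infected mothers without vertical infection as well as in children of uninfected mothers. The protocol, which was not available for this check, may recruit or match controls concurrently; recruitment in high-incidence periods within one study favors overlap. If birth dates and places do overlap, the bias is small, as the last rows of the table show.

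This stands as a limit on size. It does not remove the point. The covariate sentence and the control-group rates are permissions, not commitments, and no matching on birth date, season or center is stated in the SAP. A method built for changing incidence should not depend on the two groups happening to coincide.

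A reader might go further and infer that the trial's VTR will be several times too low or nearly twice too high. The document does not support that. Those multiples need V of about 10% or less and strongly changing incidence, and the SAP gives neither V nor Pn. They also concern V recovered from late IgG status. Children positive by PCR or IgM, meeting an agreed syndrome definition, or seen to lose IgG (including falling titers) are classified without Pn, so an overall VTR using all these routes would be affected less, by an amount the SAP does not allow one to compute.

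**Conclusion.** The point holds in conditional form. As written, Pn(t) carries age but not calendar time or center, and moves from one infant group to another, while the SAP itself says incidence varies and individualizes it for mothers only. When incidence changes across the birth period and the groups differ in birth dates or center, the antibody-based component of the VTR can be biased: downward after a passing wave or falling incidence, upward when incidence rises. Under the assumed waves the ratio of estimated to true V is about 0.7–1.4 at V = 30% and about 0.5–1.7 at V = 20%, and wider at 10% or below. It is near 1 under steady or yearly repeating incidence, or with shared birth dates and places. These figures rest on assumed V and incidence curves, on Ab = 0, and on V being recovered wholly from X(t).

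**What to change.** In X(t), and wherever V from Appendix 5 feeds Section 7.1, replace Pn(t) by a child-specific term

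Pn_i(t) = 1 − exp(−Σ λ_c(u)), summed over child i's own calendar weeks u from birth to test,

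where λ_c(u) is weekly incidence in center c, shaped by the planned surveillance series and calibrated in control infants of the same center observed over the same period. At minimum, stratify Pn by center and calendar period of birth.

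The child-level probability printed in Appendix 5, V/(V + (1−Ab(t))V), has no Pn term at all, so one must be added. The form consistent with X(t) is V/(V + (1−V)(Ab + (1−Ab)Pn_i)). At V = 10%, Ab = 0 and Pn = 5% this gives 0.10/(0.10 + 0.90×0.05) = 0.69, against 0.50 from the printed expression.

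The cost is analysis work: birth and test dates are recorded and weekly surveillance is already planned. The drawback is sparser data per center and period, which smoothing λ_c(u) over time can handle.

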### 3. Relation to ZIKA-PED, ZIKA-VID and ZIKA-SYN

#### 3.1 Outcomes of postnatal pediatric infection: ZIKA-PED.

Follow-up of postnatal infections, both primary and secondary, are within the remit of ZIKA-PED. However, postnatal infection will also be observed in ZIKA-VT. The statistical analysis of clinical symptoms and outcomes following postnatal infection seen in ZIKA-VT will be considered as part of the main ZIKA-PED analysis. However, estimation of post-natal ZIKV incidence rates in the control groups, part of ZIKA-PED, may be used to assist in the analysis of vertical transmission rates (see below and *Appendix 5*).

By the same token, after the two-year follow-up specified in ZIKA-VT, further follow-up of the three ZIKA-VT birth cohorts – Vertically Infected (VI), Maternal Infection no VI (MI – No VI), and No Maternal Infection (No MI) – will be undertaken within ZIKA-PED. However, to answer the scientific questions about outcomes of vertical infection, the statistical analysis of outcomes of vertical transmission after 2 years will be regarded as being within the remit of the ZIKA-VT statistical analysis plan. The ZIKA-PED (prospective) SAP will focus on outcomes of post-natally acquired ZIKV, which will be observed in the MI-No VI and No MI cohorts.

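### Appendix 5 gives no rule for estimating Ab(t) free of post-natal infection; if the observed control curve is used, the IgG-based part of the VTR is under-estimated

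*SAP*

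**What the plan says.** Appendix 5 of the SAP deals with infants who are still IgG+ when last seen. It uses three quantities:

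- Ab(t), defined as "the probability Ab(t) that an uninfected child born to an antibody +ve mother remains IgG+ t weeks after delivery".
- Pn(t), defined as "the probability Pn(t) that an initially IgG- newborn is IgG+ t weeks after birth as a result of a postnatal infection".
- X(t), the proportion IgG+ at t among children of women infected in pregnancy. It is built from V, Ab(t) and Pn(t), with post-natal infection added only for children who are not vertically infected and have lost maternal antibody.

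The appendix then concludes: "As we can observe Ab(t) and X(t), and we have data on and Pn(t), we can recover an estimate of V".

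On sources, Section 5.2 relies on "data on antibody loss in control children born to IgG+ mothers, and data on post-natal infection on initially IgG- newborns". Appendix 5 adds: "Data on Ab(t) will be generated from within ZIKA-VT, but we will also refer to other sources of information". Section 3.1, on post-natally acquired ZIKV, says of it: "which will be observed in the MI-No VI and No MI cohorts".

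The SAP does not say that control children are excluded, censored or modelled at post-natal infection when Ab(t) is estimated. Nor does it say how such an infection would be recognised in a child who is still IgG+.

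**The concern.** Ab(t) as defined is pure decay of maternal antibody. What can be seen in a control child of an IgG+ mother is IgG status, and post-natal infection also makes that positive. A control infected before losing maternal IgG never shows the loss. A control infected after losing it becomes IgG+ again. The SAP allows for post-natal acquisition in the exposed infants through Pn(t), but not in the controls who supply Ab(t).

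Removal of these children is not automatic. Section 5.4 says PCR has a short detection window, and Sections 5.4 and 8.2.3 put IgM persistence at about 12 weeks. An infection between visits may therefore leave only IgG, which is already present.

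The VTR is one of the two fundamental pre-specified outcomes in Section 10.4. Section 10.2 gives undetermined children a probability based on antibody persistence, Table 1 counts persistent antibody as vertical infection, and Appendix 5 says the method can be integrated into the Section 7.1 model. A bias that grows with local incidence could also look like a difference between centers. Section 4 requires estimates that stay unbiased when centers differ.

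**Working it through.** The SAP gives no figure here to reproduce. V, Pn, the incidence and the shape of the decay curve below are assumptions.

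**1. The printed equation.** X = V + (1−V)Ab + (1−V)(1−Ab)Pn, which factorises as

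1 − X = (1−V)(1−Ab)(1−Pn).

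With Ab = 0 and Pn = 0 it gives X = V, the asymptote the appendix states. Inverting,

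V = 1 − (1−X) / [(1−Ab)(1−Pn)].

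With Ab(t) as defined, this returns the true V. In a simulation of 2 million infants with Ab(t) taken only from children free of post-natal infection, V of 5%, 10%, 20% and 30% was recovered within simulation error. The equation itself needs no change.

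**2. Upper bound: every control who is IgG+ at t is counted.** The observed control curve is

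A_obs = Ab + (1−Ab)Pn, so 1 − A_obs = (1−Ab)(1−Pn).

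Entering A_obs as Ab puts (1−Pn) in the divisor twice:

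V_hat = 1 − (1−V)(1−Ab)(1−Pn) / [(1−Ab)(1−Pn)²] = 1 − (1−V)/(1−Pn) = (V−Pn)/(1−Pn).

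For V = 10%:

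| Pn(t) | Calculation | V_hat |
|---|---|---|
| 2% | 0.08/0.98 | 8.2% |
| 5% | 0.05/0.95 | 5.3% |
| 10% | 0/0.90 | 0% |

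For V = 20% the same Pn values give 18.4%, 15.8% and 11.1%.

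**3. Narrower reading: only controls continuously IgG+ are counted.** This takes the word *remains* in the definition literally. Only infections that occur before maternal antibody is lost contaminate Ab. If q is the probability of such an infection then, once maternal antibody has gone,

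V_hat = (V−q)/(1−q).

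Assumed decay: gamma loss time with shape 4 and 97.5% lost by 65 weeks, to match the 15 months in Section 5.2 (median about 27 weeks). Post-natal infection is taken at a constant rate, independent of antibody loss. Evaluation is at 104 weeks, the two-year follow-up in Section 3.1, with V = 10%:

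| Incidence per year | q | Calculation | V_hat |
|---|---|---|---|
| 1% | 0.57% | 0.0943/0.9943 | 9.5% |
| 2% | 1.13% | 0.0887/0.9887 | 9.0% |
| 5% | 2.80% | 0.0720/0.9720 | 7.4% |
| 10% | 5.50% | 0.0450/0.9450 | 4.8% |

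**4. The two readings compared.** At 5% per year, Pn at 104 weeks is 1 − exp(−0.05 × 104/52) = 9.5%. The upper bound then gives about 0.5%, against 7.4% on the narrower reading. How the control curve is tabulated therefore matters a great deal, and the SAP does not fix it.

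**5. The remedy checked.** Because 1 − X = (1−V)(1−A_obs), the control curve recovers V when modelled as what it is: V = 1 − (1−X)/(1−A_obs). This holds if exposed and control children have the same Ab(t) and the same post-natal exposure.

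**The case against.** The best defence is that the SAP prints no error in the X(t) equation. Ab(t) is defined for an uninfected child, post-natal infection enters once, and the equation returns V exactly when Ab(t) is what the definition says. This stands. A reader might infer that Appendix 5 does count post-natal infection twice. The text supports only that it would do so if the control data were used as observed, which the text invites and does not guard against.

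The wording about remaining IgG+ and about antibody loss also fits poorly with counting children who lost IgG and regained it. This stands too, so the figures in step 2 of the working are an upper bound. It does not remove the problem, because infections before antibody loss still contaminate the curve.

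Infant titers are followed, so a new infection might show as an interrupted fall, and the testing schedule may be in the protocol, which is not at hand. Some infections could be found this way. No rule in the SAP uses that information for Ab(t).

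Two further inferences are tempting and not supported:

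- **Negative VTR estimates.** The algebraic inversion goes below zero when Pn exceeds V, but Section 7 is Bayesian throughout, with V a probability under a prior. The planned model cannot return a negative value.
- **Individual infants' probabilities biased down.** The posterior printed in Appendix 5 reduces to 1/(2−Ab(t)). V cancels, and an inflated Ab(t) would raise it. That expression does not follow from the Bayes line above it and needs separate correction, but no direction of bias for infants can be drawn from it here.

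Finally, the 1% and 10% infected in Section 7.6 are illustrative maternal rates and do not support any particular Pn.

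**Conclusion.** The concern holds in a conditional form. The X(t) equation is correct, but the SAP treats Ab(t) as directly observable in children among whom it expects post-natal infection, and it gives no rule for removing or modelling that infection. Entering the observed control curve would bias the IgG-based component of the VTR downward on either reading, and more so where incidence is high.

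For an assumed true V of 10%, the estimate falls to between 8.2% and 0% at the upper bound (Pn of 2% to 10%). On the narrower reading it falls to between about 9.0% and 4.8% (incidence of 2% to 10% per year, 104 weeks, assumed decay curve).

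It should not be read as saying that the whole VTR is under-estimated by these amounts. Infants classified by PCR, IgM or antibody loss are unaffected, and the SAP does not say what share will rest on persistent IgG. The effect on the overall rate therefore cannot be sized from the document.

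**What to change.** Keep the X(t) equation. In Appendix 5:

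1. State that Ab(t) is maternal-antibody persistence in the absence of post-natal infection.
2. Estimate Ab(t), Pn(t) and V jointly, modelling the proportion of controls who are IgG+ at t as 1 − (1−Ab(t))(1−Pn(t)). Do not enter the observed control curve as Ab(t).
3. As a sensitivity check, report V = 1 − (1−X)/(1−A_obs) with controls matched on center, season and age. It needs no separate Pn, but it assumes equal post-natal exposure in exposed and control children.

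The cost is a sentence of definition and one further likelihood term for the controls in a Bayesian model already planned. No new data are needed, since the SAP already intends to collect IgG results in control children of IgG+ mothers and in initially IgG- newborns.
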